APPENDIX B

Study Diary

Study Diai y					
Name Start date				End Da	te
	Date			Time	
4 hours?	yes	no			
	1-5		6-10		11-15
nours?	yes	no			
a total of 2 complete	yes	no			
	yes	no			
	yes	no			
	Date			Time	
4 hours?	yes	no			
	1-5		6-10		11-15
nours?	yes	no			
a total of 2 complete	yes	no			
	yes	no			
	Name	Name Start date Date 4 hours? 1-5 nours? a total of 2 complete yes yes yes 1-5 nours? Date 4 hours? Date 4 hours? yes yes	Name Start date Date 4 hours? yes no 1-5 nours? yes no a total of 2 complete yes no yes no yes no 1-5 nours? yes no yes no yes no a total of 2 complete 4 hours? yes no 1-5 nours? yes no a total of 2 complete yes no	Date 4 hours? yes no 1-5 6-10 nours? yes no yes no yes no yes no yes no 1-5 6-10 Date 4 hours? Date 4 hours? yes no yes no yes no yes no yes no 1-5 6-10 nours? yes no 1-5 6-10 nours? yes no a total of 2 complete yes no	Name Start date Date Time 4 hours? yes no 1-5 6-10 nours? yes no yes no yes no yes no yes no 1-5 6-10 Time Time 4 hours? Date Time 4 hours? per no yes no yes no yes no yes no yes no 1-5 6-10 nours? yes no 1-5 6-10 nours? yes no a total of 2 complete yes no 1-5 nours? yes no

Signature/Date

To be repeated, for each day, until end of intervention

APPENDIX C

GEL APPLICATION INSTRUCTIONS:

- 1. Flammable: do not apply near fire, flame or heat, or while smoking
- 2. Apply the gel to your own breasts after bathing, preferably in the morning and at approximately the same time each day.
- 3. To apply, remove the cap from the canister. When you use a canister for the first time, you must prime it by pressing the pump fully several times until gel is dispensed (point the spout toward a sink or wastebasket and do not use the first dose, which may be incorrect).
- 4. Once the canister is primed, place it on a hard surface and place the palm of one hand under the pump to catch the gel. Be sure to press down completely on the pump and release it completely to dispense one dose of gel.
- 5. Apply a total of two complete pumps per day, one dose of gel (one complete pump) to each breast per day (dosage is indicated on the canister label). Do not apply more or less than one dose to each breast. Be sure to release the pump completely between both actuations.
- 6. If you accidentally pump twice for one breast, please discard this dose and try again to get one pump. If you press down on the pump and the gel does not fully land in your hand, please discard this dose and try again. If you do discard pumped doses, please record this on your study diary. There are extra doses in the pump to allow for priming and errors.
- 7. Spread the gel evenly over the entire surface of your breast, without rubbing.
- 8. Wash your hands immediately after applying the gel.
- 9. Allow the gel on your breasts to air dry for 2 minutes and then immediately cover with clothing (the gel is colorless and will not stain your clothing). Once dry, the gel is no longer flammable. Do not expose your bare breasts to sunlight at any time.
- 10. Do not apply any other cream, lotion or moisturizer to your breasts at any time during the study.
- 11. Do not wash your breasts or immerse in water (bath, swim) for at least 4 hours following application of the gel. If this is not possible, delay application of the gel that day until after immersion, and be sure to follow all the above instructions. If you regularly swim in the morning, it is better to apply the gel afterwards, after your shower.
- 12. After use, replace the cap on the canister.

RECOMMENDATIONS:

- 1. Be sure to apply **after bathing or showering, each day** during the study and preferably in the morning.
- 2. If you forget to apply a dose, do not double the dose to "catch up". If your next dose is scheduled within the next 12 hours, it is best just to wait; if it is more than 12 hours until your next dose, apply the dose you missed and resume your normal dosing after that.
- 3. For the duration of the study, avoid contact between the application area and the skin of other individuals (i.e. your child, your sexual partner, or other persons). If necessary, skin contact is allowable after the breasts have been washed. As noted above, you must wait at least 4 hours following application before washing the application area, otherwise, delay application until after washing and contact.
- 4. Do not ingest or swallow the gel. For external use only.
- 5. If the pump doesn't come back up correctly or if there's no gel delivered when you press down on the pump, do not use this canister and notify your doctor immediately.
- 6. After the end of study treatment, be sure to take back to your doctor **all** the gel canisters you have been given (even if empty or not used). **This is very important for the success of the study**.

STORAGE INSTRUCTIONS:

- 1. Keep your gel canisters at room temperature.
- 2. Keep the gel canisters out of the reach of children.

SPECIAL INSTRUCTIONS FOR THE DAY BEFORE SURGERY

- 1. The day BEFORE surgery, you should take your usual morning dose of the gel application. This will be your last dose of the study drug. Be sure to follow all washing instructions above.
- 2. The day of surgery, do not apply the gel. Be sure to take a shower, bathe, or wash your breasts the morning of surgery before you get to the hospital.

DELIVERY INSTRUCTIONS

Note: your institution may or may not allow for FedEx/UPS/courier delivery of gel dispensers. If you are having the dispensers delivered via FedEx, UPS, or another courier, you MUST be present to sign for the package **the first day** it arrives. If you are unable to sign for the package during the day, you have the option of requesting that the package be held for pickup.

For more information (FedEx), see: http://www.fedex.com/us/services/hold at location find locations html. For more information (UPS), see https://www.ups.com/content/us/en/register/reasons/myups.html.

APPENDI	ХD	
PID:	Visit Date:	
 		BESS Questionnair

We are interested in knowing whether you have had any of the following problems during the **PAST TWO WEEKS**. Please mark the number which best describes how much each problem bothered you.

	PROBLEM	Not at all	Slightly	Moderately	Quite a bit	Extremely
C1	Difficulty concentrating	0	1	2	3	4
C2	Easily distracted	0	1	2	3	4
C3	Forgetfulness	0	1	2	3	4
M1	Joint pain	0	1	2	3	4
M2	Muscle stiffness	0	1	2	3	4
М3	General aches and pains	0	1	2	3	4
V1	Night sweats	0	1	2	3	4
V2	Hot flashes	0	1	2	3	4
V3	Cold sweats	0	1	2	3	4
Ga1	Vomiting	0	1	2	3	4
Ga2	Nausea	0	1	2	3	4
Ga3	Diarrhea	0	1	2	3	4
D1	Vaginal dryness	0	1	2	3	4
D2	Pain with intercourse	0	1	2	3	4
W1	Weight gain	0	1	2	3	4
W2	Unhappy with the appearance of my body	0	1	2	3	4
Gy1	Vaginal discharge	0	1	2	3	4
Gy2	Genital itching/irritation	0	Ĩ	2	3	4
Gy3	Vaginal bleeding or spotting	0	1	2	3	4
В1	Difficulty with bladder control (when laughing or crying)	0	1	2	3	4

BESS Questionnaire - continued

	PROBLEM	Not at all	Slightly	Moderately	Quite a bit	Extremely
B2	Difficulty with bladder control (at other times)	0	1	2	3	4
P1	Headaches	0	1	2	3	4
P2	Blind spots, fuzzy vision	0	1	2	3	4
P3	Constipation	0	1	2	3	4
P4	Cramps	0	1	2	3	4
P5	Breast sensitivity/tenderness	0	1	2	3	4
P6	Ringing in ears	0	1	2	3	4
P7	Chest pains	0	1	2	3	4
P8	Swelling of hands or feet	0	1	2	3	4
P9	Difficulty breathing	0	1	2	3	4
P10	Dry mouth	0	1	2	3	4
P11	Weight loss	0	1	2	3	4
P12	Decreased appetite	0	1	2	3	4
P13	Feeling of suffocation	0	1	2	3	4
P14	Excitability	0	1	2	3	4
P15	Short temper	0	1	2	3	4
P16	Tendency to take naps; stay in bed	0	1	2	3	4
P17	Tendency toward accidents	0	1	2	3	4
P18	Avoidance of social affairs	0	1	2	3	4
P19	Dizziness, faintness	0	1	2	3	4
P20	Numbness, tingling	0	1	2	3	4

BESS Questionnaire - continued

P21	Early awakening	0	1	2	3	4
P22	Abdominal pain	0	1	2	3	4
P23	Pain or cramps in the legs or feet	0	1	2	3	4
P24	Back pain or problems	0	1	2	3	4
P25	Low energy	0	1	2	3	4
P26	Blurred vision	0	1	2	3	4
P27	Any other problems?	Please Spe	cify:			

Study Coordinator's Signature:	Date:
--------------------------------	-------

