5.2 Study Agent Administration

- 5.2.1 All participants will receive either active gel or placebo gel each day and will be blinded to their randomization status. The study gel will be self-administered. All subjects in Cohort 3 will receive active drug.
- 5.2.2 One 90 ml canister of gel products containing placebo or study agent will be distributed to each participant at the baseline visit. Each participant will apply the gel daily to both breasts for 21-28 days. One pump (1 mL) of placebo or active gel products will be applied to both breasts once a day. The last day of gel application will be the day prior to the day of surgery.
- 5.2.3 The gel (ENX/placebo) should be applied in the morning after daily shower (in order to minimize potential transfer to the partner at night). Participants will be instructed on application of the drug to the breasts during the initial study visit, and will apply it each morning after a shower, allow it to dry for one minute and dress as usual. If they forget to apply the gel in the morning, administration later in the day is acceptable, as long as the skin has been washed since the last application. If a dose is missed and applied late, 12 hours should elapse before application of the next dose. Participants will be instructed not to bathe, swim, or shower for at least 4 hours after gel application. Contact of other individuals with the treated breasts is unlikely to be associated with significant transfer of drug; contact is permitted after the treated area has been washed with soap and water and washing is allowable after a minimum of 4 hours post-application.
- 5.2.4 The day of surgery, participants should refrain from applying any study agent, and be sure to bathe, shower, or wash their breasts before coming to surgery, to avoid the possibility of recently applied gel contaminating the samples taken for drug assays.

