5.7 Adherence/Compliance

- 5.7.1 Compliance is defined as application of 80% of doses during the intervention period (e.g. over 28 days, 22 doses must be applied, or over 21 days, 17 doses must be applied). Additionally during the last three days of planned treatment, no doses should be missed.
- 5.7.2 Compliance will be monitored by weighing the gel canister when dispensed, and when returned at the end of the intervention. Participants will either maintain a paper study diary or use a web-app that can be accessed by either smart-phone or computer/tablet. Compliance will also be checked during weekly phone calls.
- 5.7.3 Participants who do not utilize the phone website/application will receive reminders for study medication intake via email or text messages, sent by the study staff during the first week of study and further if needed. The study staff will send emails or text message on cellular phone; participants will be encouraged to respond to these messages indicating if dose has been taken. These responses will be used to assess compliance and will be reviewed at weekly phone contact. For participants who miss more than one dose in a week, the email/text reminders will continue further into dosing period.

Participant who do utilize the phone website/application will be contacted by the study coordinator if the participant misses two or more days of entry. These responses will be used to assess compliance and will be reviewed at weekly phone contact.

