8.3 Off-Agent Criteria

Participants may stop taking study agent for the following reasons: completed the protocol-prescribed intervention, adverse event or serious adverse event, inadequate agent supply, noncompliance, concomitant medications, or medical contraindication. Participants will continue to be followed, if possible, for safety reasons and in order to collect endpoint data according to the schedule of events.

All participants included in the study who received agent may be assessed for response to intervention, Participants who complete less than 80% of the planned dose or did not take the last 3 required doses will be considered non-compliant and will not be evaluable for secondary endpoints; Participants that receive agent but withdraw without initiating treatment will be replaced and will not be followed or evaluable for DLTs.

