13.6 Reporting and Exclusions

Compliance is defined as consumption of 80% of the prescribed dose over the whole study period, and of all of the last 3 required doses. Where information is available, data on non-compliant patients will be considered for dose-response analysis. Missing data will be treated via multiple imputations as described in previous sections.

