13.8 Evaluation of Response

All participants included in the study who received agent will be assessed for response to intervention, even if there are major protocol deviations.

All of the participants who met the eligibility criteria (with the exception of those who did not receive study agent) will be included in the main analysis. All conclusions regarding efficacy will be based on all eligible participants.

Sub-analyses may be performed on the subsets of participants, excluding those for whom major protocol deviations have been identified (e.g., early death due to other reasons, early discontinuation of intervention, major protocol violations, etc.). However, sub-analyses will not serve as the basis for drawing conclusions concerning efficacy, and the reasons for excluding participants from the analysis should be clearly reported. For all measurements of response, the 95% confidence intervals will be provided.

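### Appendix C advises skipping a late-remembered dose that section 5.2.3 would accept; two or three days before surgery this costs one of the three required final doses (small effect)

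*Combined protocol and SAP*

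**What the plan says.** Section 5.2.3 asks for gel each morning. For a forgotten morning dose, "administration later in the day is acceptable, as long as the skin has been washed since the last application". It then sets the spacing: "If a dose is missed and applied late, 12 hours should elapse before application of the next dose".

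Appendix C, Recommendations, item 2 is what the participant reads. It tells her not to double up and continues: "If your next dose is scheduled within the next 12 hours, it is best just to wait". If more than 12 hours remain, she is to apply the missed dose. Under 7.2.1 item 20 this sheet is reviewed with her and dispensed with the gel.

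The end of treatment has a stricter rule. Section 5.7.1 says: "Additionally during the last three days of planned treatment, no doses should be missed". Section 13.6 defines compliance as 80% of the prescribed dose and "of all of the last 3 required doses".

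On the consequence, the sections differ. Section 8.3 says that participants who fall below 80% or "did not take the last 3 required doses will be considered non-compliant and will not be evaluable for secondary endpoints". Section 13.6 says that, where information is available, "data on non-compliant patients will be considered for dose-response analysis". Section 13.8 assesses everyone who received agent, "even if there are major protocol deviations".

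Section 3.2.1 keeps Cohort 3 on daily gel up to the day before surgery, so that drug distribution in the breast can be assessed better.

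**The concern.** Under 5.2.3 a dose remembered in the evening can be kept, and the next one moves if the 12 hours require it. Under item 2 the same dose is dropped. Early in treatment this hardly matters. On the second- or third-last dosing day (three or two days before surgery, since the last dose is on the day before), dropping it breaks the rule on the last three doses.

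Nothing else the participant is given closes the gap. The special instructions in Appendix C cover only the day before surgery and the day of surgery. The contact four days before surgery (7.3.2, with its script in Appendix E) asks her to keep applying the gel for the last three days, but does not say what to do with a late dose.

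At stake is the drug-concentration measurement for which Cohort 3 dosing was extended. A woman who does what her sheet advises can reach tissue sampling with 2 of the last 3 doses when 3 were possible.

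**Working it through.** The plan gives no figure on this point, so there is none to reproduce. The check compares the two rules by the clock and then sizes the consequence.

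**Inputs.** 8 women in Cohort 3 and 8 on active gel at 10 mg in Cohort 1 (3.2.1); 21 to 28 days of dosing (5.1); the 12-hour rules (5.2.3 and Appendix C); the 80% rule (5.7.1). The usual hour of application is not stated beyond morning, so s = 06:00, 08:00 and 10:00 are assumed.

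**1. When the rules differ.** Item 2 advises waiting from s + 12 hours until midnight, and 5.2.3 accepts the dose throughout the day. Window = 24 − (s + 12):
- s = 6: 6 hours
- s = 8: 4 hours
- s = 10: 2 hours

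Before that window the two texts agree.

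**2. Which days matter.** On the day before surgery no next dose is scheduled, so the condition in item 2 cannot be met. On the second- and third-last dosing days it can.

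**3. Exposure.** Cohorts 1 and 2 are complete. What remains is 8 × 2 = 16 woman-days. The documents give no rate of late-remembered doses. Each 1% of these woman-days on which the advice is followed gives 16 × 0.01 = 0.16 skipped doses expected.

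**4. Overall adherence after one skip.** 20/21 = 95.2% or 27/28 = 96.4%. Both exceed 80%, so only the last-three rule is broken.

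**5. Precision, if one woman were excluded.** The 95% half-width in SD units is t(0.975, n − 1)/√n:
- Cohort 3 alone: n = 8 gives 0.836 and n = 7 gives 0.925; ratio 1.106, or 11% wider.
- Cohorts 1 and 3 pooled at 10 mg: n = 16 gives 0.533 and n = 15 gives 0.554; ratio 1.039, or 4% wider.

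Pooling is plausible, because 13.5 reports by dose and Cohort 1 also dosed to the day before surgery.

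**6. What keeping the late dose does to the final dose.**
- Second-last dose late, at midnight at the latest: the final dose is due by 12:00, a shift of 12 − s = 6, 4 or 2 hours.
- Third-last dose late, at midnight at the latest: the second-last dose falls by 12:00. The gap to the usual final dose is 12 + s = 18, 20 or 22 hours, which is already at least 12, so the final dose does not move.

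**The case against.** The two texts can be read together. Section 5.2.3 grants a permission and item 2 gives advice; both protect a 12-hour gap, and Appendix C also asks for a steady time of day. A cautious sheet under a broader permission is a common choice. This stands as a reason not to call item 2 wrong for most of the treatment period. It does not cover the last days, where the sheet makes no exception and the compliance rule allows no miss.

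The reminder four days before surgery targets these days and gives a number to call. That lowers the chance of a miss but leaves the late-dose question unanswered.

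The event is also rare by construction: a woman must forget, remember only in the last 2 to 6 hours of the day, on one of two days, and then take the advice. That is right, and it is why the point is minor.

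Keeping the late dose has its own price. It can shorten the interval from final dose to tissue sampling, and the documents give no tissue half-life from which to size the effect. This stands too: a net gain in the concentration measurement is not demonstrated. What is shown is that a woman can avoid breaking the last-three rule by means that 5.2.3 already accepts.

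A reader might infer that women will drop out of the secondary analyses. The documents do not establish that. Section 8.3 points that way, 13.6 and 13.8 point the other way, and the plan does not say which governs. The 11% and 4% figures depend on that separate inconsistency.

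**Conclusion.** The mismatch is real and minor. Following the dispensed sheet on the second- or third-last dosing day produces non-compliance under 5.7.1 and 13.6 that 5.2.3 would have avoided. It concerns at most 8 women on 2 days each, and one omitted dose per event.

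Three stronger readings are not supported. The texts do not conflict throughout the day, only in the evening window. The final dosing day is not affected. The primary endpoint is not at risk, because 13.1 makes everyone who receives any study drug evaluable for skin toxicity.

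If 13.6 and 13.8 govern, no woman is lost. If 8.3 governs, and is read with 13.6 so that one missed dose of the three is enough, each such woman leaves the secondary endpoints; the first would widen the interval by 11% for Cohort 3 alone or by 4% for the pooled 10 mg group. The clock figures rest on assumed usual times of 06:00 to 10:00. No rate of forgetting is assumed.

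**What to change.** Add to Appendix C, Recommendations, item 2:

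> Two and three days before surgery, do not skip a forgotten dose: apply it later the same day to washed skin, then wait at least 12 hours before your next dose. Do not double the dose, and record the time in your diary.

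In the special instructions for the day before surgery, after the mention of the usual morning dose, add:

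> (later that morning, if needed, so that 12 hours have passed since a late dose the day before)

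Add nothing about a dose forgotten on the day before surgery itself. No dose follows it, so a 12-hour wait has no meaning there, and a general instruction to apply it late could put gel on the skin close to sampling or after the canister has been returned. Leave item 2 unchanged for earlier days.

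The cost is two short additions to the sheet for the Cohort 3 women; the diary in Appendix B already has a time field. There may be an occasional evening application, which works against the reason 5.2.3 gives for morning dosing (limiting transfer to a partner at night). Only when the second-last dose is late does the final dose move, by up to about 2 to 6 hours and to about 12:00 at the latest. That is still before canister return, which 7.2.1 places on the evening before or the morning of surgery. The interval to sampling shortens by the same amount, so the recorded time of the final dose should be reported with that woman's concentration.

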APPENDIX E

Please use the following suggested statements for participant communications.

For Email, Phone or Text Reminders during the first week (and subsequently if needed) please use the suggested statement:

"Hello my name is [insert name] from [site name/department], regarding NWU2017-09-01 TopEND research study. Please remember to apply your study gel and complete your participant diary. If you have any questions please call [insert name], Research Coordinator at (xxx) xxx-xxx."

For Phone Calls to assess compliance, toxicity, and changes in medication please use the suggested statements:

"Hello my name is **[insert name]**, Research Coordinator at (xxx) xxx-xxx from [site name/department]. I wanted to check in with you briefly about the NWU2017-09-01 TopEND study. Is this a good time to talk?"

If no: "When would be a better time for me to call you?"

If yes: "As part of your study follow up, I am calling you to briefly assess your study compliance and symptoms. Since we last spoke on <<date>>>, have you missed your study medication on any days?"

If yes: "How many days did you miss your study medication? On what dates did you miss your study medication?"

"Since we last spoke, have there been any changes to your current medications? For example, a change in dose, stopping a medication, or starting a new medication."

If yes: "Please tell me what has changed."

"Since we last spoke on <<date>>, have you noted any changes in the skin of your breast?"

If the participant reports yes, If the participant reports yes, then utilize the plain language guide below to ask more probing questions as needed.

Plain Language Guide for assessing skin application AEs

- 1. Is your breast skin dry from gel application? If yes, is it red or itchy?
- 2. Do you have pain on your breast skin? If yes, how severe?
- 3. Is your skin itchy from gel application? If yes, how severe? Are you taking any medicine for it?
- 4. Do you have rash on your breast skin? If yes, how big is the affected area? Are you taking any medicine for it? Can you please send us a picture of your rash?
- 5. Do you have hives on the breast skin where you have applied the gel? If yes, how big is the affected area? Are you taking any medicine for it?

[&]quot;Since we last spoke on <<date>>, have you experienced any other symptoms?

[&]quot;Please remember to apply your study gel and fill out the study diary. Thank you for your time."

For Reminder Phone Calls four days prior to surgery, please use the following suggested statement.

"Hello my name is [insert name] from [site name/department], regarding NWU2017-09-01 TopEND research study. This message is for [insert name]. Please remember to continue applying your study agent for the last 3 days prior to surgery and complete your participant diary. Your last gel application should be on the day before your surgery. If you have any questions please call [insert name], Research Coordinator at (xxx) xxx-xxx."

For the Last Phone Call to premenopausal women, please use the following suggested statement:

"Hello my name is [insert name] from [site name/department], regarding NWU2017-09-01 TopEND research study. Is this a good time to talk?"

If no: "When would be a better time for me to call you?"

If yes: "Have you had a period since we last met? If so, what was the start date?"

"Thank you for your time and for participating in this study."

